#### **9.4.2 Comparison of baseline characteristics**

Baseline comparison of the treatment groups with regard to demographic variables will be compared with general used tests.

#### **9.4.3 Primary study parameter(s)**

A poisson regression model was used to analyse the primary outcome measure, evaluating both events and exposure (person-time), employing a quasilikelihood factor (with overdispersion correction), and incorporating the following covariables: treatment assignment, age, sex, smoking history, and presence of *P aeruginosa* and azithromycin maintenance use at baseline.

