### 4.2 Inclusion criteria

In order to be eligible to participate in this study, a subject must meet all of the following criteria:

1. Age  $\geq$  18 years
2. The presence of chronic respiratory symptoms such as cough, dyspnoea, expectoration of sputum
3. Confirmed non-CF bronchiectasis by (HR)CT
4. Documented history of at least 2 pulmonary exacerbations treated with courses of antibiotics within 12 months before inclusion.
5. No course of antibiotics or maintenance antibiotics (except for macrolides) 1 month prior to the start of the study.
6. Minimal one documented sputum or BAL-fluid culture with gram-negative bacteria or *S. aureus* within 12 months.
7. Growth of protocol defined pathogens in sputum

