#### **4.4 Sample size calculation**

The hypothesis is that prolonged treatment with tobramycin reduces the number of exacerbations per patient by 50%. This reduction seems clinically relevant and is based on the assumption that maintenance treatment with TIS OD as well as intermittent TIS BID is comparable to that of azithromycin treatment. This assumption is derived from the data of the BAT trial (placebo: mean 2,1 exacerbations (sd 1.6); azithromycin: mean 0,8 exacerbations (sd 1.1). The reduction in percentage is used for the determination of trial size.

We used a poisson regression model to determine group size. For type I error and type II error 0.05 and 0.2 were used respectively. The hypothesis will be tested two sided. With a baseline exacerbation rate of 2.1 in the placebo group and an expected response rate ratio of 0.5 with an exposure time of 1 year a total of 18 evaluable patients are required to be on each treatment arm.

With a drop-out percentage of 30% we must include totally 48 (24 patients per group) patients.

Due to unforeseen reasons we initially include two extra patients per group. But after the interim analysis three extra patients will be included in the study, because the drop-off percentage is higher as expected in advance. Reason for discontinuation of the study is the intensive treatment and cleaning schedule of the inhaled study medication. So, with a total of 58 patients (29 per group) with bronchiectasis, and not the initially 52 patients (26 per group), we expect to achieve the intended effect size.

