## **7.3 Study procedures**

Patients with bronchiectasis and who fulfil the inclusion and exclusion criteria will be asked to participate in the study. After a run-in period of 4 weeks' patients will be randomized to receive one of the two possible treatment regimens: TIS OD 300 mg daily or placebo. Administration will be continuous for the full 12 months. According to the parallel group design patients will be treated for 52 weeks. After completing the intervention period patients will have a follow-up (wash out period) of 4 weeks. This wash-out period was considered to be one month, in which time the antimicrobial effect of the antibiotic supposedly disappears, as suggested in earlier studies.

Subjects will be evaluated at run-in = visit 0 (week -4), visit 1 (day 1- start of the study), visit 2 (week 13), visit 3 (week 26), visit 4 (week 39), visit 5 (week 52: end of treatment) and visit 6 (run-out; week 56: end of the study). One week after start of treatment a phone call will be scheduled. Clinical, laboratory, and bacteriology evaluations will be determined according to the schedule (Figure 1: study schedule). Subjects who terminate treatment should be followed for the same period as those who complete the study, according to the study schedule.

During the study any changes in medical condition and compliance with medication will be filed in the diary card.

At visit 1, after randomisation, a tolerance test with either TIS or placebo (blinded according to randomisation) will be performed. Before nebulizing TIS patients are treated with salbutamol 200mcg using an AeroChamber. During tidal breathing patients inhale 300mg TIS or placebo (at room temperature) by using the Innospire Deluxe nebulizer with mouthpiece during approximately 5 minutes. If patients develop a moderate-severe bronchial obstruction, patients are excluded from the study. The severity of bronchial obstruction and coughing is assessed by a specialized nurse, the respiratory physician or the own GP. An exacerbation is defined as the presence of three or more of the following symptoms or signs for at least 24 hours: increased cough, increased sputum volume, increased sputum purulence, haemoptysis, increased dyspnoea, increased wheezing, fever (>38.5°C)

or malaise, and the treating physician agreed that antibiotic and/or prednisolone therapy was required.

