#### **Run-in (Visit 0, week -4)**

At the baseline visit (- 4 weeks), subjects will be deemed eligible for the study after the clinical diagnosis bronchiectasis has been made, and the study has been explained to them. The following procedures will be completed:

- Verify inclusion/exclusion criteria
- Obtain written informed consent (alternatively at visit 1)
- Record medical history
- Collection of demographic information, concurrent disease, concomitant medication use, and previous course(s) of antibiotic therapy in the preceding year
- Physical examination (including sputum characteristics, cough, dyspnoea, pleuritic chest pain, chills or rigors, and lung sounds) and vital signs (respiratory rate, heart rate, blood pressure, body temperature and oxygen saturation)
- Laboratory examination (CRP, Hb, WBC, Sodium, Potassium, Creatinin, eGFR, Liver Function Tests, extra blood sample(s) will be taken and frozen for future research)
- Sputum culture (semi-quantitative)
- Randomisation (or at visit 1)

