#### **9.4.6 Interim analysis**

After inclusion and follow up of 50% of the randomized patients an interim analyses will be conducted. A poisson regression model is used for our power analysis; See chapter 9.1.

The interim analysis is used to calculate the predetermined effect size, and whether more patients should be included depending on this effect size. Depending on the frequency of exacerbations at baseline and the effect size, a power analyses will be done by using the poisson regression model.

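### The primary model and the randomisation both leave out prior-year exacerbation frequency, so a chance imbalance in it would go uncorrected in a 58-patient trial

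*Combined protocol and SAP*

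**What the plan says.** The primary outcome is the number of exacerbations per year. Section 9.4.3 analyses it with a Poisson model that accounts for person-time and corrects for overdispersion, "incorporating the following covariables: treatment assignment, age, sex, smoking history". The list then adds presence of P. aeruginosa and "azithromycin maintenance use at baseline", and stops there.

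Sections 7.2 and 9.2 describe 1:1 allocation and name no stratification factor.

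Information on the previous year is gathered. Section 4.2 requires "Documented history of at least 2 pulmonary exacerbations treated with courses of antibiotics within 12 months before inclusion". The visit 0 and visit 1 procedures in section 7.3 both record "previous course(s) of antibiotic therapy in the preceding year". Section 9.4.6 ties the interim power calculation to exacerbation frequency at baseline ("Depending on the frequency of exacerbations at baseline and the effect size"). That phrase could equally mean the control-group rate, so nothing here rests on it.

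**The concern.** How often a patient exacerbated last year is the pre-treatment measurement closest to the endpoint. The plan already adjusts for five baseline variables but not for this one, and allocation does not balance it by design. In a trial of 58 patients, one arm can by chance receive the more frequent exacerbators, and part of that difference would then be read as treatment effect, or would hide one. If the imbalance is discovered only after unblinding, adding the covariate is post hoc and leaving it out invites a challenge to the result. A line written beforehand avoids both.

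**Working it through.** **The plan's own figure.** Inputs from sections 4.4 and 9.1: placebo rate 2.1, rate ratio 0.5, exposure 1 year, overdispersion 1.0, two-sided alpha 0.05, power 80%. The Poisson-regression formula with a 50:50 binary covariate gives

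N = [1.960 × √4 + 0.842 × √(2 + 2/0.5)]² / (2.1 × (ln 0.5)²) = 35.46,

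rounded up to 36, or 18 per arm. This reproduces the plan.

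**How much patients differ.** The documents give no correlation between prior-year and on-study counts, so this must be assumed. For a gamma-Poisson count, k = (SD² − mean)/mean². The means and SDs quoted in section 4.4 give:
- placebo: (2.56 − 2.1)/4.41 = 0.104
- azithromycin: (1.21 − 0.8)/0.64 = 0.64

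The range used is k = 0.10 to 0.64. Each simulated patient has a stable rate, enters with a prior count of at least 2, and the underlying mean m is set so that the on-study placebo rate is 2.1.

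**How often the arms differ.** The simulated prior count has SD 1.20 at k = 0.10 and 1.42 at k = 0.64. With 29 per arm:
- k = 0.10: SE = 1.20 × √(2/29) = 0.315; 2 × [1 − Φ(0.5/0.315)] = 0.11
- k = 0.64: SE = 1.42 × √(2/29) = 0.373; 2 × [1 − Φ(0.5/0.373)] = 0.18

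Simulation agrees, at about 11-19% of allocations.

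**What a difference does.** In this model the expected on-study rate rises by km/(1 + km) per prior exacerbation. For a gap of exactly 0.5:
- k = 0.10, m = 1.927: slope 0.193/1.193 = 0.162; shift ln(1 + 0.5 × 0.162/2.1) = 0.038
- k = 0.64, m = 1.303: slope 0.834/1.834 = 0.455; shift ln(1 + 0.5 × 0.455/2.1) = 0.103

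Averaged over simulated trials with a gap of 0.5 or more, the unadjusted log rate ratio shifts by about 0.03-0.05 at k = 0.10 and 0.10-0.15 at k = 0.37-0.64. With log(prior count) in the model the shift is about 0.02 or less. The standard error of the log rate ratio is about 0.24 at k = 0.10 and 0.28 at k = 0.64, so the largest shifts are about 0.05/0.24 = 0.2 and 0.15/0.28 = 0.5 of a standard error. On the ratio scale, a true 0.50 would be estimated on average at 0.50 × e^±0.05 = 0.48 or 0.53, and at 0.50 × e^±0.15 = 0.43 or 0.58.

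**Average precision and power, 29 per arm.** Variance ratio is adjusted over unadjusted; power is without → with log(prior count).

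| k | Implied placebo SD | Variance ratio | Power, no other covariates | Power, five other covariates |
|---|---|---|---|---|
| 0.10 | 1.57 | 1.02 | 84.3% → 83.9% | 80.1% → 79.4% |
| 0.15 | 1.62 | 1.00 | 82.9% → 83.1% | not run |
| 0.30 | 1.72 | 0.98 | 78.3% → 79.7% | not run |
| 0.37 | 1.76 | not run | not run | 72.4% → 73.8% |
| 0.64 | 1.86 | 0.95 | 72.7% → 75.4% | 69.6% → 72.7% |

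The third and fourth columns use 4,000 runs per setting, the last 6,000. Overall type I error was 4.6-5.5% with or without the covariate. At 18 per arm and k = 0.10, power goes from 63.2% to 61.7%, a loss of 1.5 points. That these powers fall below the plan's 80% at 18 per arm comes from the overdispersion in the simulation and the Wald t-test, and is a separate matter.

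**The case against.** The strongest reply is that at the only placebo SD the documents quote, the covariate buys nothing on average. Variance does not fall, power slips slightly, and an imbalance of 0.5 moves the estimate by about a sixth of a standard error. The larger shifts need more heterogeneity than that placebo arm shows; k = 0.64 comes from the treated arm of another trial. This stands. It limits the size of the point and rules out calling it a power gain.

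The covariate is also not the endpoint measured earlier. Entry sets a threshold of 2, so the count is truncated. The explicit data item is antibiotic courses, with no indication stated. The on-study definition in section 7.3 needs at least three symptoms for 24 hours and that "the treating physician agreed that antibiotic and/or prednisolone therapy was required", which admits prednisolone-only events. A reader might infer that the trial already holds a baseline version of its endpoint. The documents support only a derivable proxy, and because the simulation assumes identical definitions and a stable patient rate, its benefits are optimistic.

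The plan already includes P. aeruginosa, which section 1 links to worse disease, and a sixth baseline covariate is a burden in a small trial. This is fair, but none of the listed variables measures exacerbation frequency, and the cost is small.

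Finally, sections 4.4 and 9.1 already report a consequence of the interim analysis, and section 9.4.6 has that analysis estimate the effect size. A model change made now could itself be called data-driven. This is a reason to control who makes the change and when.

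**Conclusion.** The omission is real and worth correcting as cheap protection against an unlucky allocation. About 11-19% of allocations at 29 per arm would differ by 0.5 or more prior exacerbations. The consequence is small (0.03-0.05 on the log rate ratio) if patients are as homogeneous as the quoted placebo SD suggests, and moderate (0.10-0.15, up to about half a standard error) at k = 0.37-0.64. The documents do not settle which applies.

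Two stronger conclusions are tempting and unsupported. One is that the planned test is invalid; overall type I error stays near 5% without the covariate. The other is that precision is being given away; the average power change is about -1 to +3 points, with no precision gain at the quoted placebo SD. Nor do the documents show that any imbalance has occurred.

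The figures rest on a gamma-Poisson model, stable patient rates, the same event definition before and after entry, and no dropout.

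**What to change.** Before unblinding, add to the section 9.4.3 covariate list the log of the number of antibiotic-treated exacerbations in the 12 months before inclusion. State that the count is taken from the entry-criterion documentation and the visit 0 and 1 record of antibiotic courses. Note that it is a proxy, truncated at 2 and limited to antibiotic-treated events, for the on-study definition. Because of the interim analysis, date the change and have it made by people who have not seen exacerbations by arm.

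The cost is a line or two of wording and one degree of freedom, with no new assessments. If patients are nearly homogeneous it loses about 1 power point at 29 per arm and up to 1.5 at 18 evaluable per arm. Using the same covariate in the Cox model of section 9.4.4 is optional; its effect there was not quantified.

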#### **9.4.4 Secondary study parameter(s)**

Time to first exacerbation during the treatment period, as well as during the wash-out period, will be assessed using Cox proportional hazards regression and reported graphically using Kaplan-Meier estimates.

Statistical significance in change of FEV1 (percent of predicted) and FVC (percent of predicted) attributable to treatment will be calculated with a linear mixed-model analysis. The effect of time on outcome variables will be checked for linearity by means of plots and model Proportional hazards assumptions will be tested with log-minus-log plots. Time will be entered as an interval variable, with the number of intervals depending on the frequency of follow-up visits at which the outcome will be measured. Predefined confounders are entered stepwise as fixed effects. Predictors remain in the regression equation if the model fit increases significantly. Thereafter, random effects will be explored for intercept (patients) and slope (time and patients). If random effects do not change the model fit significantly, a fixed effect will be assumed. Change in quality of life was analyzed using linear mixed-model analysis as well. The minimal important difference (MID) in bronchiectasis was reported only for the Quality Of Life-Bronchiectasis questionnaire (QOL-B), with a minimal important difference (MID) for the Respiratory symptoms scale of 8 points represent clinical relevance. The MID for the leicester cough questionnaire in chronic cough is 1.3 points in total and represent clinical relevance. The Leicester cough questionnaire was initially developed for patients with chronic cough, but has been validated in patients with bronchiectasis. Consequently, the minimal important difference of 1.3 points will be used in this study and represent clinical relevance. Secondary to these questionnaires the LRTI-VAS questionnaire will be used. This questionnaire is a validated and reliable tool for symptom measurement in non-CF bronchiectasis.

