## SUMMARY

**Rationale:** Patients with bronchiectasis often have exacerbations of their disease. These exacerbations influence the quality of life. In patients with cystic fibrosis (CF) longterm inhaled antibiotics lower the bacterial load in bronchial secretions and have positive effect on the number of exacerbations, lung function and quality of life (QoL). In patients with non-CF bronchiectasis colonized with *Pseudomonas aeruginosa* studies with tobramycin inhalation solution (TIS) are limited, however with only five trials to date. In present study the value of maintenance TIS will be investigated in patients with non-CF bronchiectasis colonized by different bacterial species sensitive for tobramycin.

**Objective:** The primary outcome of the study is a 50% reduction in exacerbation rate in patients using maintenance TIS (OD). Secondary outcome parameters are lung function (FEV1, FVC), QoL (QOL-B), LTRI-VAS, Leicester cough score, bacterial load in sputum and tobramycin resistant pathogens.

**Study design:** A randomised, double blind placebo controlled, multicenter study.

**Study population:** Patients aged  $\geq 18$ -year-old with confirmed bronchiectasis by (HR)CT and at least two exacerbations during previous 12 months.

**Intervention (if applicable):** During the study each group (placebo, intervention) receives TIS or placebo, once daily 300mg/5ml for at least 9 months and up to 12 months.

**Main study parameters/endpoints:** The primary endpoint is a reduction of exacerbations that patients suffer during the treatment period. Next to this parameter we expect to show a significant beneficial effect on lung function parameters, QoL, bacterial load of pathogens in sputum and tobramycin resistance.

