## 9. STATISTICAL ANALYSIS

### 9.1 Calculation of study numbers

See 4.4. sample size calculation

We used the Poisson regression model for the power analysis:

Numeric Results when X1 is Binomial with Proportion = 0,5 And Phi (Over-Dispersion Parameter) = 1,0000

	Mean R-Squared							
	Sample Size (N)	Response Rate Ratio	Baseline Rate Exp(B0)	Exposure Time (MuT)	X1 vs Other X's (R2)	Two-Sided Alpha	Beta	
Power	0,80000	36	0,5000	2,1000	1,0000	0,0000	0,05000	0,20000

The hypothesis is that prolonged treatment with tobramycin reduces the number of exacerbations per patient by 50%. This reduction seems clinical relevant and is based on the assumption that maintenance treatment with TIS OD as well as intermittent TIS BID is comparable to that of azithromycin treatment. This assumption is derived from the data of the BAT trial (placebo: mean 2,1 exacerbations (sd 1.6); azithromycin: mean 0,8 exacerbations (sd 1.1)). The reduction in percentage is used for the determination of trial size.

We used a poisson regression model to determine group size. For type I error and type II error 0.05 and 0.2 were used respectively. The hypothesis will be tested two sided. With a baseline exacerbation rate of 2.1 in the placebo group and an expected response rate ratio of 0.5 with an exposure time of 1 year a total of 18 evaluable patients are required to be on each treatment arm.

With a drop-out percentage of 30% we have to include totally 48 (24 patients per group) patients10:22. Due to unforeseen reasons we initially include two extra patients per group. But after the interim analysis three extra patients will be included in the study, because the drop-off percentage is higher as expected in advance. Reason for discontinuation of the study is the intensive treatment and cleaning schedule of the inhaled study medication. So with a total of 58 patients (29 per group) with bronchiectasis, and not the initially 52 patients (26 per group), we expect to achieve the intended effect size.

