### **9.4 Methods of analysis**

#### **9.4.1 General statistical considerations**

All data will be collected and analysed using SPSS statistics 20.

Statistical analysis will be performed on an intent-to-treat basis by the investigator and an independent statistician. All continuous variables will be tested for normal distribution with the Kolmogorov-Smirnov test for normal distribution. The Student-t test will be used for normally distributed variables, the Mann-Whitney U test for not normally distributed variables and the  $\chi^2$  test for dichotomous variables. The software package SPSS 20 for Windows (IBM-SPSS Inc., Chicago, Illinois, USA) is available for statistical analysis. A value of  $p < 0.05$  will be considered significant.

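### The Cox model planned for the 4-week wash-out would rest on about 5 to 7 first events with no defined risk set, and it is one of about nine secondary tests each called significant at p < 0.05

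*Combined protocol and SAP*

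**What the plan says.** Section 9.4.4 sets out two analyses of time to first exacerbation in one sentence: "Time to first exacerbation during the treatment period, as well as during the wash-out period, will be assessed using Cox proportional hazards regression". Section 7.3 fixes the length of the second period: "After completing the intervention period patients will have a follow-up (wash out period) of 4 weeks". No event count, power, time origin or risk set is given for the wash-out model.

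Section 9.4.1 has one rule for all tests: a p-value below 0.05 "will be considered significant". Section 7.1.2 lists eight secondary outcomes: time to exacerbation, FVC, FEV1, LRTI-VAS, QOL-B, Leicester cough score, sputum bacterial load and tobramycin resistance. The separate wash-out model makes nine tests. The plan contains no hierarchy, adjustment or exploratory label. The Summary shows that significance claims are intended: "Next to this parameter we expect to show a significant beneficial effect on lung function parameters", and it continues with quality of life, bacterial load and resistance.

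On follow-up, 9.4.1 specifies intention-to-treat, and 7.3 and 7.6 have patients who stop treatment followed on the full schedule to week 56. Sections 3 and 5.3 are weaker. They encourage withdrawn patients to stay, but accept as a minimum a final assessment done as an early termination visit. Section 7.3 also removes from the study, after randomisation, patients who develop moderate-severe obstruction at the tolerance test.

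**The concern.** Four weeks is 4/52 of a year, in a trial of 58 patients sized on a full year of events. A hazard ratio from so short a window carries almost no information about what happens after stopping TIS, yet the plan treats it like any other test.

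The comparison also lacks a stated risk set. The plan does not say whether patients who left the study, stopped drug months earlier, or had already exacerbated before week 52 count as at risk in wash-out. The Summary and Section 3 allow 9 to 12 months of treatment, while 7.3 has the full 12, so even the start of wash-out need not be common to all patients.

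At stake is the reading of the secondary results. Under 9.4.1, any of about nine results could be reported as significant on its own, with no control of error across the set.

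**Working it through.** **Inputs.** From 4.4: "With a baseline exacerbation rate of 2.1 in the placebo group and an expected response rate ratio of 0.5"; "For type I error and type II error 0.05 and 0.2 were used respectively"; "The hypothesis will be tested two sided"; 18 evaluable patients per arm; 30% drop-out. From Section 3: 29 randomised per arm. From 9.1: "Phi (Over-Dispersion Parameter) = 1,0000". From 7.3: wash-out of 4/52 = 0.0769 year.

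**1. The plan's own figure.** The documents give no figure for the wash-out model, so the check on the inputs is the primary sample size. For Poisson regression with a balanced binary covariate, the null variance term is 4 and the alternative term is 2 + 2/0.5 = 6:

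N = (1.96 × √4 + 0.8416 × √6)² / (2.1 × (ln 0.5)²) = 35.5, rounded up to 36.

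This reproduces the stated 36 (18 per arm).

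**2. Expected first events in wash-out.** With constant rates, the probability of a first event in 4 weeks is:

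- placebo: 1 - exp(-2.1 × 0.0769) = 0.149
- TIS, rate ratio still 0.5: 1 - exp(-1.05 × 0.0769) = 0.0776

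| Patients per arm | Rate ratio 0.5 persists | Rates equal after stopping |
|---|---|---|
| 29 | 4.33 + 2.25 = 6.6 | 8.7 |
| 24 | 5.4 | 7.2 |
| 20.3 (29 less 30%) | 3.03 + 1.58 = 4.6 | 6.1 |
| 18 | 4.1 | 5.4 |

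If only patients still exacerbation-free at week 52 were at risk, 29 per arm would give 29 × (exp(-2.1) × 0.149 + exp(-1.05) × 0.0776) = 1.3 events. For contrast, a Cox model from randomisation through a full 52 weeks would have 29 × (1 - exp(-2.1)) + 29 × (1 - exp(-1.05)) = 25.4 + 18.9 = 44.3.

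**3. Precision.** The 95% interval extends by a factor exp(1.96 × √(1/d₁ + 1/d₂)) either side of the estimate:

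- 29 per arm: exp(1.96 × √(1/4.33 + 1/2.25)) = 5.0
- 20.3 per arm: exp(1.96 × √(1/3.03 + 1/1.58)) = 6.9

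Counting all events instead of first events (4.68 v 2.34, and 3.28 v 1.64) gives 4.8 and 6.5.

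**4. Power.** By the Schoenfeld approximation, power at hazard ratio 0.5 is Φ(√(D/4) × 0.693 - 1.96). That is 12% at D = 5, 13% at D = 6 and 15% at D = 7. Simulated log-rank power is 14% at 29 per arm and 10% at 20 per arm. For 80% power, D = 4 × (1.96 + 0.8416)² / (ln 0.5)² = 66 events. With 5 to 7 events, p < 0.05 needs an estimate of about exp(-1.96 × 2/√D) = 0.17 to 0.23 or more extreme. A significant result in the planned direction would therefore overstate a true 0.5 at least twofold.

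**5. Familywise error.** For nine independent tests, 1 - 0.95⁹ = 37.0%. Simulating nine equally correlated normal statistics gives 33%, 27% and 20% at correlations 0.3, 0.5 and 0.7. Without the wash-out test, 1 - 0.95⁸ = 33.7%.

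**The case against.** The best defence is that these are secondary analyses under a single primary outcome, where unadjusted p-values are common. It adds that the plan specifies intention-to-treat with follow-up to week 56 and announces no carry-over or rebound claim. That is fair, and it keeps the point small. It does not supply a risk set, and it does not square with a Summary that expects significant secondary effects.

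Several stronger readings are tempting, and the documents do not support them.

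- A reader might infer that a false secondary claim is likely. At 20-37% the chance is substantial but stays below one half.
- A reader might infer that few events inflate the false-positive rate. Under the null, the simulated log-rank test with about 4 to 9 expected events rejected in 3.9-5.2% of runs. Sparse data cost precision and power. Dropping the wash-out test lowers the familywise error by only 3.3 points (37.0% to 33.7%), so the multiplicity remedy lies mainly in 9.4.1.
- A reader might infer that the wash-out model is confined to a non-randomised subset of completers. Section 9.4.4 does not say so, and 7.3 and 7.6 point the other way. What stands is that the risk set is undefined. It is probably selected, given the early termination visits accepted in Sections 3 and 5.3, the tolerance-test removals in 7.3, and the higher than expected drop-out reported in 4.4.
- A reader might infer that recently treated exacerbations, being commoner on placebo, would protect that arm and mimic a rebound on stopping TIS. No section supports such protection. Even if it were complete, 15% of placebo and 8% of TIS patients would have had an exacerbation in the preceding 4 weeks. That moves a hazard ratio of 1 only to 0.92/0.85 = 1.08, which is negligible beside an interval factor of 5 or more.

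**Conclusion.** The point holds as a modest, inexpensive improvement. The wash-out Cox model would have about 5 to 7 first events (4.1 to 8.7 over 18 to 29 patients per arm and rate ratios of 0.5 or 1). With 5 to 7 events it has 12-15% power at a hazard ratio of 0.5, and its interval spans a factor of about 5 to 7 either side. It cannot support a conclusion in either direction, and its risk set is not defined. Separately, the 9.4.1 rule leaves a familywise error of about 20-37% across the secondary tests.

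These figures assume constant exacerbation rates at the planning values, 30% drop-out, and one test for each listed outcome plus the wash-out model. Testing MIC values, individual QOL-B scales or several visits separately would raise the number of tests. The primary analysis is not affected.

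**What to change.** In 9.4.4, limit the Cox model to time from randomisation to first exacerbation through week 52. State that exacerbations in the 4-week wash-out will be reported as counts and person-time by arm, with the number of patients contributing, and without a hypothesis test.

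In 9.4.1, reserve the word significant for the primary analysis in 9.4.3. State that all secondary results will be given as estimates with 95% confidence intervals and nominal p-values. Bring the Summary's sentence on expected secondary effects into line.

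This takes about two sentences and needs no extra patients, visits or data. The cost is fewer secondary claims.
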